7. SAFETY ANALYSIS

Safety endpoints include AEs, clinical laboratory variables, vital signs, and ECG variables.

Unless otherwise specified, all safety analysis will be performed by study part and treatment group for the safety set.

7.1 Adverse Events

Adverse events (AEs) will be coded using the most recent version of MedDRA (version 23.0). Adverse event severity level will be classified into mild, moderate, severe by investigators. For incidence summaries, a missing severity of an AE will be conservatively imputed as severe. Handling rules for missing severity of AEs are described in Section 12.6.5.

AEs are classified as related to study drug if AEs are definitely or possibly related to study drug. Any AEs with missing or unknown relationship will be considered as related to study drug (Section 12.6.6).

Treatment emergent adverse events (TEAEs) are defined as those AEs that develop or worsen in severity after the first dose of study drug and up to 30 (+7) days beyond the last dose of study drug.

All summaries of AEs described in this section will be on TEAEs. An overall summary of the number of subjects with TEAEs as well as the total number of events will be presented, including the number and percentage of subjects with

- any TEAEs,
- treatment-emergent serious adverse events (SAEs),
- treatment-related TEAEs,
- treatment-related SAEs,
- infusion site reaction TEAEs,

Clinical Protocol APL9-COV-201

Apellis Pharmaceutical, Inc Statistical Analysis Plan V2.0

- TEAEs leading to dose modification (dose reduction or interruption),
- TEAEs leading to treatment discontinuation,
- TEAEs leading to study discontinuation,
- TEAEs leading to death.

The number and percentage of patients reporting TEAEs will be tabulated by SOC and PT; by SOC, PT, and maximum severity.

In summary, the following types of tables will also be provided:

- TEAEs by SOC and PT
- TEAEs by SOC, PT and maximum severity
- Treatment-emergent SAEs by SOC and PT
- Treatment-related TEAEs by SOC and PT
- Treatment-related SAEs by SOC and PT
- Infusion site reaction TEAEs by SOC and PT
- TEAEs leading to dose modification by SOC and PT
- TEAEs leading to treatment discontinuation by SOC and PT
- TEAEs leading to study discontinuation by SOC and PT
- TEAEs leading to death by SOC and PT

If a SOC or PT was reported more than once for a subject, the subject would only be counted once in the incidence for that SOC or PT. For subjects experiencing the same PT at multiple severities, the occurrence of the AEs with the maximum severity will be counted in the analysis of incidence by severity. For subjects experiencing the same PT at multiple relationship levels, the occurrence of the AEs with the strongest relationship to study drug will be counted in the analysis of incidence by relationship to study drug.

The following listing will be provided for the Safety Population:

- All AEs
- Serious Adverse Events
- AEs leading to dose modification
- AEs leading to treatment discontinuation
- AEs leading to study discontinuation
- AEs leading to Death

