### 11.2.5. Recording AEs

Adverse events and SAEs will be collected from the signing of the consent form up to and including the safety follow-up assessment 30 days after the last dose of study drug (up to Study Day 51 with a +7-day window).

Any events that occur prior to dosing will be categorized as pretreatment events; events occurring after dosing will be recorded as TEAEs (start date of dosing and, therefore, categorization of the event will be dependent on randomization assignment).

For each AE, the investigator will evaluate and report the onset date (and time if applicable), resolution date (and time if applicable), intensity, causality, action taken, serious outcome, and whether or not it caused the subject to discontinue the study.

If possible, the outcome of any AE that caused permanent discontinuation or was present at the end of the study should be reported, particularly if the AE was considered by the investigator to be related to the investigational product. Subjects experiencing AEs that cause interruption or discontinuation of investigational product, or those experiencing AEs that are present at the safety follow-up assessment (30 days after the last dose of APL-9), up to and including Study Day 51 (+7) should receive follow-up as appropriate.

All SAEs must be reported to the sponsor/Apellis Safety via eCRF immediately and within 24 hours of becoming aware of the event, whether or not the event is deemed treatment-related. If the electronic data capture system is not operational (or for paper-based study[ies]), the site must complete the paper SAE form and email to PPD \_\_\_\_\_\_, also within 24 hours of becoming aware of the event. The reported information submitted as a paper SAE must be entered into the electronic data capture system once it becomes operational.

Adverse events will be coded in accordance with the Medical Dictionary for Regulatory Activities (MedDRA). If known, the diagnosis of the underlying illness or disorder should be recorded, rather than its individual symptoms.

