## 12.4. Safety Analysis

All safety analyses will be summarized for the safety set.

Adverse events will be coded using MedDRA. All AEs, including TEAEs, will be summarized by System Organ Class, Preferred Term, and treatment group for number of subjects and proportion reporting the event. A similar summary will be produced for SAEs, AEs leading to termination, severe AEs, and AEs related to the investigational product. The intensity of AEs and the relationship to investigational product will be summarized for each System Organ Class and Preferred Term by treatment group.

Withdrawals because of AEs will be summarized for each body system and Preferred Term by treatment group.

As described in Section 11.2, TEAEs are defined as those AEs that develop or worsen after the first dose of study medication up to and including the safety follow-up assessment 30 days after the last dose of study drug (up to Study Day 51 with a +7-day window).

AE summaries will be presented across all subjects. All AEs will be listed by subject, along with information regarding onset, duration, relationship, and severity to investigational product, action taken with investigational product, treatment of event, and outcome.

All laboratory assessments will be summarized by treatment group using appropriate descriptive statistics.

Changes from baseline in clinical laboratory tests will be summarized, using descriptive statistics, by visit and nominal time after dosing, and by treatment group. Baseline will be taken as the last predose assessment. Out-of-range values will be flagged in data listings.

Changes from baseline in vital signs will be summarized, using descriptive statistics, by treatment, visit, and nominal time after dosing. Baseline will be taken as the last predose assessment.

Values of potential clinical significance will be flagged in listings and summarized by treatment.

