2.2 Endpoints

2.2.1 Primary Objective Endpoint

 Cumulative incidence of treatment-emergent serious adverse events (SAEs) and treatmentemergent adverse events (TEAEs)

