Subjects may receive treatment beyond Day 7 if the DMC approves an extended treatment duration following the review of data from Part 1 or during the conduct of Part 2. The DMC may approve any extended treatment duration up to and including Day 21; extended treatment will be allowed

only in subjects who still require respiratory support (oxygen supplementation or mechanical ventilation) at Day 7 with an improved PaO2/FiO2 ratio of at least a 20mm Hg from baseline if arterial blood gas (ABG) test results are available for comparison. If ABG test results are not available, an improvement in FiO2 of at least 4% in nonventilated patients (eg, those on nasal cannula) and 10% in mechanically ventilated patients is needed. FiO2 should be weaned following the site's protocol to keep oxygen saturation at 89% or above. Treatment beyond Day 7 and up to and including any DMC-approved extension will be at the discretion of the investigator.

Follow-up safety assessments for each subject will be collected 30 days following the last dose of study treatment (up to and including Study Day 51 with a +7-day window). Safety assessments may be performed any time during the 30-day follow-up period at the investigator's discretion but are required 30 days after the last dose of study drug (up to and including Study Day 51 with +7day window). These assessments will be conducted via inpatient assessment (for subjects still hospitalized) or by telephone call (for subjects discharged).

The DMC will perform safety and efficacy data reviews on an ongoing basis during Part 2. Two reviews will be required in Part 2:

- After the 10th subject reaches the approved treatment duration, discontinuation of respiratory support (oxygen supplementation or mechanical ventilation), or hospital discharge, whichever occurs latest
- After the 30th subject reaches the approved treatment duration, discontinuation of respiratory support (oxygen supplementation or mechanical ventilation), or hospital discharge, whichever occurs latest

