12. DATA HANDLING CONVENTIONS

12.1 General Data Reporting Conventions

Categorical variables will be tabulated as number of subjects and percentage of total number of subjects in the given analysis set as noted for each category. Percentages will be reported to one decimal place.

Descriptive statistics will be used to summarize continuous variables including number of subjects, mean, standard deviation (SD), median, first quantile (Q1), third quantile (Q3), minimum, and maximum. Mean, median, Q1 and Q3 will be reported to 1 more decimal place than the raw data, while the SD will be reported to 2 more decimal places than the raw data. Minimum and maximum will be reported the same as the original data.

In general, all analyses will be performed by study part and treatment groups unless otherwise specified. Subject specific listings will be provided by study part, treatment, subject ID, visit and date, if applicable.

All summaries and statistical analysis will be performed by SAS v9.4 or later.

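### TEAEs are counted to 30 (+7) days after each subject's own last dose, so Part 2 arms treated for different lengths of time are compared over unequal time at risk

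*SAP*

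**What the plan says.** The primary objective is the safety of APL-9 compared with vehicle. SAP 2.2.1 names the endpoint as the cumulative incidence of treatment-emergent SAEs and TEAEs.

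- **Window.** SAP 7.1 counts events that start or worsen after first dose and "up to 30 (+7) days beyond the last dose of study drug". Protocol 12.4 ties the window to the same visit: "TEAEs are defined as those AEs that develop or worsen after the first dose of study medication up to and including the safety follow-up assessment", which falls 30 days after last dose. Collection stops there too (Protocol 11.2.5): "Adverse events and SAEs will be collected from the signing of the consent form up to and including the safety follow-up assessment".
- **Summary.** SAP 7.1: "An overall summary of the number of subjects with TEAEs as well as the total number of events will be presented". The denominator is set in SAP 12.1: "Categorical variables will be tabulated as number of subjects and percentage of total number of subjects in the given analysis set". Kaplan-Meier, log-rank and Cox methods appear only in SAP 6.2.1, for efficacy endpoints. SAP 5.6 tabulates treatment duration, but no adverse event table uses it.
- **Treatment length in Part 2.** SAP 3.1: "The DMC may approve any extended treatment duration up to and including Day 21". Two conditions apply to the subject: still needing respiratory support at Day 7, and being "with an improved PaO2/FiO2 ratio of at least a 20mm Hg from baseline" (or, without blood gas results, a set improvement in FiO2). The investigator then decides.

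**The concern.** The length of the counting window is fixed by something that happens after randomization. Day 7 respiratory status, an outcome that the drug is meant to influence, helps decide whether a subject is dosed and observed for up to 14 more days. Randomization does not balance that.

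No test of TEAEs is planned, so the side-by-side percentages are the primary result. If one arm is extended more often, part of any difference in those percentages, and in total event counts, reflects observation time rather than the drug. No planned table lets a reader separate the two.

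**Working it through.** **The plan's own figures.** SAP 3.2 gives the chance of seeing at least one SAE among 30 subjects as 1 − (1 − p)^30. For p = 1%, 4%, 7% and 10% this is 26.0%, 70.6%, 88.7% and 95.8%, matching the stated 26%, 71%, 89% and more than 95%. These figures treat incidence as one number per subject and attach no time horizon to it.

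**Time at risk.** With first dose on Day 1 and last dose on Day L, the window holds L + 30 days.

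- L = 7: 37 days (44 with the full +7)
- L = 21: 51 days (58 with the full +7)
- Ratio: 51/37 = 1.38, or 58/44 = 1.32 when both have the +7

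**Effect on a percentage at equal hazard.** Assume a constant hazard, the same in both arms, and let P be the incidence by Day 37. Then F(w) = 1 − (1 − P)^(w/37). The documents give neither a TEAE incidence nor extension shares, so both are assumed over a range. If shares e1 and e2 of the two arms are extended to Day 21, the false difference is (e1 − e2) × [F(51) − F(37)].

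| P by Day 37 | F(51) | 50% vs 20% extended | 40% vs 30% extended | All vs none |
|---|---|---|---|---|
| 10% | 13.5% | 1.1 points | 0.4 | 3.5 |
| 30% | 38.8% | 2.7 | 0.9 | 8.8 |
| 50% | 61.5% | 3.5 | 1.2 | 11.5 |
| 70% | 81.0% | 3.3 | 1.1 | 11.0 |

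One subject of 30 is 3.3 points. At 50% versus 20% extended, mean time at risk is 44.0 versus 39.8 days (0.5 × 51 + 0.5 × 37, and 0.2 × 51 + 0.8 × 37). That is 10.6% longer, so under the same assumption expected total events are also 10.6% higher.

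**The +7 days.** Given to every subject, the comparison is F(58) with F(44). For P = 30%, 50% and 70%, F(44) is 34.6%, 56.2% and 76.1%, and F(58) is 42.8%, 66.3% and 84.8%. At 50% versus 20% extended the false difference is 2.5, 3.0 and 2.6 points.

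**If events cluster early.** Let the hazard after Day 14 be a quarter of the earlier hazard. Cumulative hazard is then proportional to 14 + 0.25 × 23 = 19.75 by Day 37 and 14 + 0.25 × 37 = 23.25 by Day 51. P = 30% becomes 34.3% rather than 38.8%, and the 50% versus 20% difference is 0.3 × 4.3 = 1.3 points.

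**If no extension is approved.** With last dose anywhere from Day 1 to Day 7, windows run only from 31 to 37 days before the +7.

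**The case against.** The case for leaving the plan as it is has several good points.

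- **Direction.** A reader might infer that the count is biased against APL-9, because improvers are extended. The documents do not support that. Extension needs continued respiratory support as well as improvement, so a drug that frees subjects from support by Day 7 makes them ineligible. Benefit could raise or lower the extension share.
- **Deaths.** A reader might also infer that delaying death inflates the APL-9 percentage. For any TEAE and any SAE it does not: under Protocol 11.2.2 an adverse event resulting in death is serious, so a subject who dies of one in the window already counts in both. The issue is confined to specific non-fatal terms. Treating death as a competing event does not remove it there, since the incidence of non-fatal events still rises when deaths fall.
- **The +7 days.** Comparing Day 58 with Day 37 would give 4.9 points at P = 50%. That grants the extra week only to extended subjects. Granted to all, it slightly reduces the difference.
- **Size.** At the SAE incidences in SAP 3.2 (1% to 10%), 50% versus 20% extended gives only 0.1 to 1.1 points.
- **Terminology.** A proportion over a stated period is a cumulative incidence. The name is not the problem; the period differing between subjects is.
- **A fixed Day 37 is not free.** Subjects who stop dosing before Day 7 may have collection end before Day 37. A subject dosed to Day 21 has only 16 days after last dose by then.

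All of this stands and limits the point. None of it gives the arms equal time at risk when their treatment lengths differ.

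**Conclusion.** The point holds in conditional form: if the Part 2 arms differ in treatment length, the planned percentages favour the shorter-treated arm at equal hazard, and nothing in the SAP corrects for it. Which arm that would be cannot be told from the documents.

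Under a constant hazard with 50% versus 20% extended, the distortion is about 1 to 3.5 points across 10% to 70% incidence. It reaches about 9 to 12 points only if every subject in one arm and none in the other is extended, at 30% to 70% incidence. It shrinks if events come early and largely disappears without an approved extension. Because no TEAE test is planned, it affects the descriptive reading of the primary endpoint and not a type I error rate. It merits a change because the change is cheap, not because the distortion is likely to be large.

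**What to change.** In SAP 7.1, keep the existing last-dose-window tables and add, for Part 2, for any TEAE and any SAE:

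1. The cumulative incidence of first event by Study Day 37 in both arms, whatever the last dose date. Censor subjects whose event collection ends earlier at that point, and treat death as a competing event for non-fatal events.
2. Exposure-adjusted rates, as events per 100 subject-days at risk.

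State that the between-arm comparison rests on the common-time figures. Item 1 should lead, because a rate is free of the window's length only under a constant hazard. In the early-clustering example above, the average hazard is 23.25/51 = 0.46 of the early hazard over 51 days and 19.75/37 = 0.53 over 37 days, so the longer-observed arm would show the lower rate.

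The cost is SAP wording and two added tables or sets of rows, built from onset, dosing and survival dates that are already collected. Dosing, visits and sample size do not change. There are two drawbacks. Some subjects who stop early are censored before Day 37, possibly for reasons related to outcome, so their number per arm should be shown. Events after Day 37 in extended subjects appear only in the last-dose-window tables and the rates, which is why those tables must stay.

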7.2 Clinical Laboratory Data

The detailed lab parameter list is summarized in Table 2 (Page 47) of study protocol APL9-COV-201 amendment 3. Continuous laboratory parameters will be normalized by converting values in original units to values in SI units and classified as normal, abnormal low, or abnormal high on normal ranges supplied by the local laboratories and upon employing standardization.

Observed values and change from baseline of clinical laboratory data (serum chemistry, hematology, coagulation, complement activation and inflammation, and continuous urinalysis parameters) will be summarized at each analysis visit. Categorical laboratory data will also be tabulated by the number and percentage of patients of each category at each analysis visit.

Frequency of abnormal (out-of-range) laboratory values will be tabulated by analysis visit.

If lab values are beyond detectable limit, the detectable limits will be used for analysis. The original collected values will be presented in the listings.

Clinical laboratory data will be presented in listings. Out of range laboratory results with their corresponding changes from baseline will be listed in separate listings.

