#### 11.1.8. Clinical Laboratory Tests

Laboratory test samples (Table 2) are to be obtained at designated visits as detailed in the SoA (Table 1). Blood will be collected 3 times on Day 1: (1) once prior to administration of the APL-9 bolus, (2) once as soon as possible following the bolus (within 5-10 minutes) prior to the continuous infusion, and (3) once at 2 hours after the beginning of the continuous infusion. Following that, assessments should be collected within the time frame of each calendar day.

Blood samples will be analyzed at one or more central (or local) laboratory facilities, as defined in the laboratory manual. All laboratory reports must be reviewed, signed, and dated by the investigator. A legible copy of all reports must be filed with both the subject's eCRF and medical record (source document) for that visit. Any laboratory test result considered by the investigator to be clinically significant should be considered an AE (clinically significant AEs include those that at minimum require an intervention). Clinically significant abnormal values occurring during the study will be followed up until repeat test results return to normal, stabilize, or are no longer clinically significant.

Instructions for collection, handling, processing, storage, and shipping of samples will be provided in a separate laboratory reference manual prior to study initiation.

PARAMETERS ANALYZED AT	THE LOCAL LABORATORY	
Blood/serum/plasma samples		
Hematology	Serum chemistry	
ABG	Albumin	Ferritin
Hb	ALT	Glucose
Hematocrit	ALP	Haptoglobin
Platelet count	AST	HDL
RBC count	Bicarbonate	Iron
Reticulocyte count	Bilirubin (total, direct, and indirect)	LDH
Schistocytes	BUN	LDL
WBC count with differential	C-reactive protein (CRP)	Phosphorus
	C3 and C4	Potassium
Coagulation panel a	Calcium	Pregnancy
D-dimer	Chloride	Sodium
Fibrinogen	Creatinine	Total cholesterol
INR	Creatine kinase	Total protein
PT	Cystatin C	Triglycerides
	eGFR	Troponin
		Uric acid
Urine samples		
Urinalysis		
Bilirubin		Nitrite
Blood		pН
Glucose		Protein
Ketones		Specific gravity
Leukocyte esterase		Urobilinogen
-	sediment, including for presence of	
	performed on all abnormal urinalyses	
Respiratory swab	· · · · · ·	
Viral RNA or viral antigen assessme	nt	
SARS-CoV-2		
PARAMETERS ANALYZED AT	CENTRAL/SPECIALTY LABORATO	RIES
Plasma samples		
Complement biomarkers	Inflammation biomarkers CC	
Bb, C3a, C4a, C5a, TCC	TNFα	
	IL-1β	
	IL-6	
Serum samples		
PK concentrations		
AH50		

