9. PHARMACODYNAMIC ANALYSIS

9.1 Pharmacodynamic Data

The pharmacodynamic (PD) endpoints will be evaluated using the PD Population.

Observed values, changes from baseline and percentage changes from baseline in PD endpoints will be summarized by study part and treatment group at each protocol specified time point using descriptive statistics. PD markers include the following:

- complement activation (C3, C3a, C4, C4a, Bb, C5a, TCC, and alternative complement pathway hemolytic activity [AH50]),
- coagulopathy (reticulocyte count, schistocytes, lactate dehydrogenase, D-dimer, ferritin, haptoglobin, fibrinogen),
- inflammatory cytokines (C-reactive protein, tumor necrosis factor α , IL-1 β , and IL-6).

Spaghetti plots for individual observed values and individual changes from baseline will be presented graphically. Actual sampling times will be used for the graphical presentation of individual data

Observed values, changes from baseline, and percentage changes from baseline will also be presented graphically by study part and treatment group. Nominal sampling times will be used for the display in plots.

PD parameters will be listed together with changes from baseline and percentage changes from baseline by study part and treatment group.

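### SAP 7.2 tabulates out-of-range laboratory values by visit without the baseline category, so subjects who newly go out of range are counted by arm only if the abnormality became a TEAE

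*SAP*

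**What the plan says.** SAP 7.2 has each continuous laboratory value "classified as normal, abnormal low, or abnormal high on normal ranges supplied by the local laboratories". It then plans four outputs:

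- observed values and change from baseline at each visit;
- counts per category at each visit for categorical tests;
- the out-of-range table: "Frequency of abnormal (out-of-range) laboratory values will be tabulated by analysis visit";
- listings, one of which links abnormality to baseline: "Out of range laboratory results with their corresponding changes from baseline will be listed in separate listings".

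SAP 7 makes the tables by study part and treatment group. For laboratory data, Protocol 12.4 asks for descriptive summaries, including change from baseline, and for out-of-range flags in the listings. Neither document plans a baseline-by-post-baseline table or a count of treatment-emergent laboratory abnormality.

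Laboratory findings can also reach the AE tables. Protocol 11.1.8 states: "Any laboratory test result considered by the investigator to be clinically significant should be considered an AE". Protocol 11.2.1 adds changes that lead to stopping study drug, and says that where a diagnosis explains the values, only the diagnosis is reported. SAP 7.1 defines TEAEs as "those AEs that develop or worsen in severity after the first dose of study drug".

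For vital signs, SAP 7.3 sets thresholds in its Table 2 and uses them to flag values in a listing. Protocol 12.4, directly after its vital-sign paragraph, says potentially significant values will be both flagged and summarized by treatment. SAP 14.1 reports no changes from the protocol's analyses.

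**The concern.** Safety is the primary objective, and the primary endpoint is the incidence of SAEs and TEAEs. A laboratory change that is neither judged clinically significant nor a cause of stopping study drug does not enter that endpoint. The range-based laboratory tables are the evidence that does not depend on those routes, so they should show new abnormality plainly.

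The by-visit table does not. It mixes subjects who were abnormal at entry with subjects who became abnormal on treatment. It also does not show whether successive visits count the same people. Abnormality at entry is to be expected: the population has respiratory failure from COVID-19, and the kidney and liver exclusion requires both a low eGFR and a high ALT, so a subject with only one of them can enrol. A reader of the planned tables could not say how many subjects per arm moved from normal to abnormal in, for example, ALT or creatinine.

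**Working it through.** **The plan's own figure.** The only sample-size figure is the chance of at least one SAE among about 30 subjects, 1 − (1 − p)^30. For p = 1%, 4%, 7% and 10% this gives 26.0%, 70.6%, 88.7% and 95.8%, which matches SAP 3.2. It does not bear on the laboratory tables, but it supplies n = 30 per arm. The documents give no laboratory abnormality rates, so every rate below is an assumption.

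**Does another output give the count?**

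- Change from baseline is summarized with "mean, standard deviation (SD), median, first quantile (Q1), third quantile (Q3), minimum, and maximum" (SAP 12.1). None of these counts subjects who cross a limit.
- The listings are ordered by part, treatment, subject and visit (SAP 12.1). They hold the information, but it must be counted by hand.
- SAP 9.1 adds percentage change and individual plots ("Spaghetti plots for individual observed values and individual changes from baseline will be presented graphically") for listed markers. Protocol Table 2 has 8 hematology, 4 coagulation and 31 chemistry lines, 43 in all. Dropping ABG and pregnancy, and counting C3 and C4 separately, gives 43 − 2 + 1 = 42 local blood tests. SAP 9.1 covers 10 of them: seven coagulopathy markers, CRP, C3 and C4. ALT, AST, bilirubin, creatinine, eGFR, troponin, hemoglobin and platelets are not among them.
- SOFA change (SAP 6.2.2) includes creatinine, bilirubin and platelets, but only within a total score.
- The TEAE tables count subjects once per preferred term, by arm, for new or worsened events. This is a count of the required kind, limited to abnormalities reported as AEs.

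**Bound on the hidden count.** Suppose all 30 subjects in an arm are measured, with k out of range at baseline and at each of v later visits. The number newly abnormal lies between 0 and min(30 − k, v × k). With k = 3 and v = 3 (Days 3, 5 and 7), that is 0 to min(27, 9) = 9. The low end is the same 3 subjects each time. The high end is 3 different, previously normal subjects at each visit. The table reads 3/30 = 10% throughout in both cases.

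**Dilution of a true difference.** Let p be the share out of range at a visit through worsening, whatever the baseline; b the share abnormal at baseline; and r the share of the other baseline-abnormal subjects who have normalized, taken as equal in both arms. Then:

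visit rate = p + b(1 − p)(1 − r)

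difference = (p1 − p0)[1 − b(1 − r)]

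Take p1 = 0.40 on APL-9 and p0 = 0.15 on vehicle, a true difference of 25 points. For example, at b = 0.3 and r = 0 the visit rates are 0.40 + 0.3 × 0.60 = 0.580 and 0.15 + 0.3 × 0.85 = 0.405, a difference of 17.5 points.

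| b | r = 0 | r = 0.5 | r = 1 |
|---|---|---|---|
| 0.1 | 22.5 | 23.75 | 25 |
| 0.3 | 17.5 | 21.25 | 25 |
| 0.5 | 12.5 | 18.75 | 25 |
| 0.8 | 5 | 15 | 25 |

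**Is a shift count sharper?** The table below gives the exact binomial probability that the APL-9 count does not exceed the vehicle count (lower is better). The by-visit table uses 30 per arm. The shift count uses only the 30(1 − b) subjects normal at baseline, at 40% versus 15%.

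| b | by visit, r = 0 | by visit, r = 0.5 | by visit, r = 1 | shift count (n per arm) |
|---|---|---|---|---|
| 0.1 | 0.042 | 0.029 | 0.018 | 0.024 (27) |
| 0.3 | 0.107 | 0.056 | 0.018 | 0.044 (21) |
| 0.5 | 0.189 | 0.089 | 0.018 | 0.083 (15) |
| 0.8 | 0.356 | 0.146 | 0.018 | 0.246 (6) |

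The shift count is clearly better at r = 0 and slightly better in three of the four r = 0.5 cases. It is worse in the other 5 of 12: all four at r = 1, and b = 0.8 at r = 0.5.

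**The case against.** The strongest reply is that the plan already covers the important cases. A laboratory abnormality that matters clinically, or that stops treatment, becomes an AE and is counted by arm in the TEAE tables. The listings identify the subjects, and with about 30 per arm they can be read. SAP 7.2 also goes beyond Protocol 12.4, which asked only for flags on out-of-range laboratory values. By the figures above, the existing table is the sharper comparison in 5 of 12 scenarios. A shift table has a blind spot too: a subject already high at baseline who rises tenfold stays in the high-to-high cell.

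Most of this stands, and it rules out three stronger readings that a reader might infer.

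- *The plan has no by-arm count of new laboratory abnormality at all.* The TEAE tables are such a count for abnormalities reported as AEs. Investigator judgment is not the only route in, because Protocol 11.2.1 also covers changes that lead to discontinuation.
- *The by-visit comparison is biased.* The arms are randomized, so it is a fair comparison of who is out of range on that day. As a reading of new abnormality it is diluted.
- *A shift table would detect more.* Its gain is the visible count.

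What the reply does not remove is the range-based abnormality that never became an AE, which no table counts against baseline.

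On vital signs, the SAP states that it supersedes the protocol's analysis plan. It may therefore drop the summary, but SAP 14.1 should then say so.

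**Conclusion.** The point holds as a low-cost improvement; no planned laboratory analysis is incorrect. Apart from TEAEs, the number of subjects per arm who newly went out of range cannot be read from any planned table. In the worked case it could be anywhere from 0 to 9 of 27. The dilution figures (a 25-point difference showing as 5 to 25 points) rest on assumed rates and on equal normalization in both arms. If normalization differed between arms, the visit difference would mix onset with recovery.

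The vital-sign point is a separate mismatch and is wrong as written: the protocol promises a by-treatment summary, the SAP plans only a listing flag, and SAP 14.1 records no change.

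The ECG table in SAP 7.4 also ignores baseline, but it reports a reader's interpretation and interval changes are already summarized, so that gap is minor.

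**What to change.** **SAP 7.2.** Keep the by-visit table. Add by-arm shift tables from baseline category to worst post-baseline category, with the low and high directions shown separately. Print the number normal at baseline as the denominator, and the number of draws per subject by arm. State whether the two post-dose Day 1 draws count as post-baseline. Note that worsening within an already abnormal category is still read from the change summaries and listings.

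**SAP 7.3.** Add a by-treatment count of subjects who meet the vital-sign criteria in SAP Table 2 after baseline. State whether the observed-value and change columns must both be met. Alternatively, record the omission in SAP 14.1.

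**SAP 7.4 (optional).** Cross-tabulate ECG interpretation by baseline interpretation.

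**Cost.** SAP wording, one shift layout repeated for about 40 analytes, and one vital-sign count. No new data or thresholds are needed, because range categories and baseline are already defined. The drawback is that worst-value counts rise with the number of draws, which varies with length of stay and treatment extension. That is why draws per arm should be printed alongside.
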